7.5 STUDY PERIOD I: ON-THERAPY PERIOD (MONTHS 1 TO 12)

The 24-month study treatment period will be divided into two 12-month periods: the On-therapy Period during which subjects receive protocol therapy (ARN-509 monotherapy, ARN-509 + LHRHa, or LHRHa monotherapy). Subjects will commence protocol therapy on Day 1 of the On-therapy Period. The study timeline is defined as Day 1 = first dose of study treatment. Subsequent study time points will be defined based on study calendar, irrespective of subsequent dose delays/interruptions (see Section 9 for discussion of dose delays due to toxicity).

Subjects will be treated with protocol therapy for 12 months, or until disease progression (either by PSA or radiographic), unacceptable toxicity, subject/physician withdrawal, or initiation of non-protocol therapy. PSA progression is defined as an increase in PSA to $> 50\%$ of the baseline value or an increase of > 2 ng/mL above the nadir, whichever is higher confirmed by repeat measurement at least 2 weeks later. Radiographic progression is defined as the detection of new metastasis on either bone scan or cross-sectional imaging (CT or MRI) [61]. If subjects develop progressive disease (either by PSA or radiographic) while receiving protocol therapy, they will discontinue protocol therapy, have a Progression Visit, and be treated as per individual investigator discretion.

If there is no evidence of disease progression (by serum PSA or radiographically) after 12 months of protocol therapy or if subject discontinues treatment before 12 months of protocol therapy for reasons other than disease progression, subjects will enter the 12-month Off-therapy Observation Period. Continuation of hormone therapy or initiation of any form of anti-cancer

therapy in the absence of PSA or radiographic progression will be considered non-protocol therapy and will result in study removal.

Efforts will be made to ensure that subjects who develop progressive disease before 12 months of therapy still complete QOL scales at 3 and 12 months.

7.5.1 Day 1 of Study Treatment

Subjects will return to study site for a history and physical exam including weight, measurement of serum PSA, and dispensing of study drug(s), including the first injection of LHRHa and 1 month supply of ARN-509 for subjects randomized to those arms. Collection of optional samples (samples for banking, archival FFPE blocks or slides for transcriptome profiling (RNAseq), whole blood for RNA testing, and plasma for biomarker testing) should occur before predose.

7.5.2 LHRH Agonist

For subjects randomized to either the LHRHa monotherapy or the LHRHa + ARN-509 combination treatment arms, the choice and schedule of LHRHa will be up to individual investigator's discretion and will be administered for a total of 12 months of therapy in the absence of disease progression or unacceptable toxicity. No change in dosing schedule of LHRHa will be permitted once the subject has commenced protocol therapy. For example, the use of an every 3 month subcutaneously injected LHRHa would be administered on Day 1 and on Months 3, 6, and 9. The use of LHRH antagonists (ie, degarelix) will not be permitted as outlined in Section 6.2.1. No dose reductions or interruptions of LHRHa will be permitted (see Section 9.3). If a subject does not receive a scheduled LHRHa injection within ± 7 days of the scheduled due date for injection, he will be removed from study. Subjects on the LHRHa monotherapy arm will not be allowed to crossover to receive ARN-509.

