3 STUDY DESIGN

3.1 OVERALL STUDY CHARACTERISTICS

This is a Phase 2, randomized, open-label 3-arm multicenter study evaluating 12 months of treatment with an LHRHa monotherapy, ARN-509 monotherapy, or the combination in men with non-metastatic biochemically relapsed prostate cancer with rapidly increasing PSA levels after prior definitive therapy for localized prostate cancer. The two experimental arms (ARN-509 monotherapy; ARN-509 + LHRHa) will each be compared with a control arm of standard androgen deprivation (LHRHa monotherapy). Subjects will be stratified by PSADT (< 6 months vs. 6-12 months) and age (≤ 70 vs. greater than 70) and randomized with equal probability (1:1:1 ratio) from within each of the four strata to one of the 3 study arms.

There will be 2 treatment periods of 12 months each (24 months):

- (1) On-therapy Period lasting 12 months, during which time subjects receive randomly assigned protocol therapy
- (2) Off-therapy Observation Period from months 13 through 24

Subjects who develop progressive disease (either by serum PSA or radiographic progression) at any time during the 2 study periods will be removed from the study and will be treated as per individual investigator discretion. Subjects who discontinue before completion of the On-therapy Period in the absence of progressive disease will enter the Off-therapy Observation Period of the study. If subjects do not have evidence of PSA or radiographic progression at the end of 24 months, they will remain on study, enter a Follow-up Period, and be followed until PSA or radiographic progression or initiation of non-protocol therapy. Non-protocol therapy is defined as re-initiation of hormonal therapy or initiation of other anti-cancer therapy. The total study duration is 6 years from the date of first subject enrolled once the Off-therapy Observation Period has been completed. Subjects in the Follow-up Period will be discontinued at the time of the final clinical cutoff as described in Section 11.2.2.

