¹Pre-study assessments need to be completed within 14 days prior to randomization. Day 1 must occur within 5 calendar days of randomization.

²Subjects who discontinue during the On-therapy Period in the absence of progressive disease will enter the Off-therapy Observation Period of the study (see schedule below). If at any time a subject initiates a non-protocol therapy, the subject will be removed from study and treated as per individual investigator discretion.

³In addition to the end of each month visit assessments. Window for all visits is during treatment is ± 2 days. Window for laboratory assessments before study visits is -7 days.

⁴Complete these assessments if a subject develops PSA or radiographic progression before the end of Month 12. The subject will then be removed from study and treated as per individual investigator discretion

⁵Choice of LHRHa is per investigator's discretion. The first dose of ARN-509 or LHRHa will be on Day 1. ARN-509 will be administered daily with or without food. All subjects should be following a 28-day, 28-day, 35-day schedule for their monthly visit (i.e., the 1st post-Day 1 visit is scheduled for 28 days later, the 2nd post-Day 1 visit is scheduled for 28+28 days later, the 3rd post-Day 1 visit is scheduled for 28+28+35 days later, the 4th post-Day 1 visit is scheduled for 28+28+35+28 days later, etc). If a subject does not receive a scheduled LHRHa injection within ± 7 days of the scheduled due date for injection, he will be removed from study

⁶Physical exam changes will not be collected in the eCRF, any change in physical exam from baseline needs to be recorded on the adverse event page

⁷Adverse event collection starts from signing the ICF. For subjects who discontinue therapy and do not proceed to the Off-therapy Period, AEs must be recorded up to 30 days after the last dose of study medication.

⁸See Section 7.5.4.

⁹Scans need to be done within 6 weeks prior to randomization. At the Progression Visit, scans may be omitted if already done within the prior 1 month.

¹⁰At the Progression Visit, may be omitted if already done with the prior 1 month.

¹¹For reference, see, <https://www.shef.ac.uk/FRAX/tool.aspx?country=9>. DEXA scan is also to be used for osteoporosis assessment.

¹²DEXA scan needs to be done within 12 weeks prior to randomization. At Progression Visit, scans may be omitted if already done within the prior 1 month.

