7.5.6 QOL

The FACT-P, EORTC QLQ-C30/QLQ-PR25, and SHIM questionnaires will be completed at the end of Month 3 and Month 12 or at the time of PSA or radiographic progression (if occurs before Month 12, every effort will be made to obtain the 12-month questionnaires for those who discontinue before 12 months).

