10.4 ADMINISTRATION OF QOL QUESTIONNAIRES

The aforementioned questionnaires (FACT-P, EORTC QLQ-C30/QLQ-PC25 and SHIM) will be administered to each subject according to the study schedules (see Sections 7.1 and 7.2). The questionnaires should take approximately 20-30 minutes to complete. A designated clinical research coordinator will ensure that subjects complete the questionnaires during their study visit. If a subject stops protocol therapy due to unacceptable toxicity or progressive disease, effort will be made to ensure that subjects continue to complete QOL questionnaires according to the study schedule.

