1.2 Trial Design

This is a randomized, multicenter, open-label, 3-arm phase 2 clinical trial evaluating 12 months of treatment with luteinizing hormone releasing hormone agonist (LHRHa) monotherapy, apalutamide monotherapy, or the combination of apalutamide and LHRHa, in men with non-metastatic BCR prostate cancer with rapidly rising PSA levels after prior definitive therapy for localized prostate cancer. Enrollment of approximately 90 subjects (30 per arm) is planned for this study. Patients will be followed for safety and efficacy as per the schedule of assessments and will remain on study treatment until the time of PSA or radiographic progression or initiation of non-protocol therapy or subject/physician withdrawal from the study, whichever occurs first. Subjects will be stratified by PSADT (< 6 months vs. 6-12 months) and age (≤ 70 vs. > 70). There will be 2 periods of 12 months each in the 24-month-long treatment period: 1) an on-

therapy period lasting 12 months, during which time subjects receive randomly assigned protocol therapy, and 2) an off-therapy observation period also lasting 12 months. If there is no evidence of PSA or radiographic progression after 24 months from Day 1 of the on-treatment period, subjects will enter a follow-up period. Subjects will remain on study until the time of PSA or radiographic progression or initiation of non-protocol therapy or subject/physician withdrawal from the study, whichever occurs first. Patients who discontinue before completion of the on-therapy period in the absence of progressive disease will enter the off-therapy observation period of the study.

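### An LHRHa injection outside its ±7-day window takes a man off study, so PSA and testosterone follow-up can be cut short in the LHRHa arm but never under ARN-509 alone

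*Protocol*

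**What the plan says.** **Removal rule.** Protocol 7.5.2 covers both LHRHa-containing arms. If an injection is not given within ±7 days "of the scheduled due date for injection, he will be removed from study". Footnote 5 to the on-therapy schedule (7.1) and SAP 2.2.2 say the same.

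**Observation rule.** Protocol 3.1: "Subjects who discontinue before completion of the On-therapy Period in the absence of progressive disease will enter the Off-therapy Observation Period". Protocol 7.5: "if subject discontinues treatment before 12 months of protocol therapy for reasons other than disease progression, subjects will enter the 12-month Off-therapy Observation Period". SAP 1.2: "Patients who discontinue before completion of the on-therapy period in the absence of progressive disease will enter the off-therapy observation period of the study". Schedule footnote 2 agrees, and 7.8 promises efforts to move such men into observation or follow-up.

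**Stated exception.** Under 7.5, continuing hormonal treatment, or starting any anti-cancer "therapy in the absence of PSA or radiographic progression will be considered non-protocol therapy and will result in study removal". Footnote 2 carries a similar exception. Neither names a missed injection window, and 7.8 does not list one among its reasons for stopping treatment.

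**QOL after stopping.** Protocol 7.5.6 says that "every effort will be made to obtain the 12-month questionnaires for those who discontinue before 12 months", whatever the reason. Section 10.4 is narrower: "If a subject stops protocol therapy due to unacceptable toxicity or progressive disease, effort will be made to ensure that subjects continue" with the questionnaires.

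**The concern.** The two rules give different answers for a man who misses the window, stops LHRHa and has not progressed. One ends his participation. The other gives him PSA and testosterone every two months (7.6.3). No text says which prevails, so sites could act differently.

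The consequence is one-sided in one comparison. A man on ARN-509 alone receives no injections and cannot trigger the rule. His drug may be delayed or reduced (7.5.3, 9.2), and a delay beyond 28 days for adverse events may at most meet a criterion for stopping treatment, after which the observation rule applies. In ARN-509 alone versus LHRHa alone, this rule can therefore shorten follow-up only among controls. Hypothesis 1 (2.1) looks to comparable PSA suppression in that comparison to support further study of ARN-509 monotherapy, so control-arm PSA data have some weight even though the endpoints are exploratory.

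**Working it through.** **1. Endpoints, one at a time (ARN-509 alone versus LHRHa alone)**

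| Endpoint | Handling | Effect of removal |
|---|---|---|
| Time to PSA progression | SAP Table 1 censors a man without progression at his last PSA | Earlier censoring |
| Progression-free with testosterone > 150 ng/dL at 24 months | Protocol 11.4.2 and SAP 5.3.1.2 leave out men who withdraw before 24 months | Leaves the denominator if removal counts as withdrawal, which the text does not settle |
| PSA < 0.2 ng/mL after 7 months | Similar approach (SAP 5.3.1.2); no imputation planned (SAP 5.1.2) | No value if removal comes earlier |
| Time to testosterone recovery | Compares only the two LHRHa arms; most early discontinuers already excluded | Not one-sided |
| Month-12 FACT-P (primary) | 7.5.6 seeks the score; ITT set; a Month-3 score still enters the MMRM | Small |

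Protocol 6.4.2.3 describes the first three as exploratory.

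**2. The plan's own power figure**

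Inputs (Protocol 11.1): 27 evaluable per arm, difference 7.5, SD 8.7, two-sided 0.025. For a two-group t test the noncentrality is 7.5 / (8.7 × √(1/27 + 1/27)) = 3.17 on 52 degrees of freedom, giving 80.2% power. The stated 80% reproduces.

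As a worst case, suppose every removed control also lacks Month-12 FACT-P, beyond the planned 10% loss:

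| Extra control losses | n (ARN-509 vs LHRHa) | Power |
|---|---|---|
| 0 | 27 vs 27 | 80.2% |
| 1 | 27 vs 26 | 79.3% |
| 2 | 27 vs 25 | 78.4% |
| 4 | 27 vs 23 | 76.3% |

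**3. How many men might be removed**

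The documents give no missed-window rate. Assume a chance q of missing each later injection and k later injections; expected removals per LHRHa arm are 30 × (1 − (1 − q)^k). With k = 3 (the three-monthly example in 7.5.2):

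- q = 1%: 30 × (1 − 0.99³) = 0.9
- q = 2%: 30 × (1 − 0.98³) = 1.8
- q = 5%: 30 × (1 − 0.95³) = 4.3

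The dosing schedule is left to the investigator. Over q = 1% to 5%, one later injection gives 0.3 to 1.5 removals and eleven give 3.1 to 12.9. The count for ARN-509 alone is zero throughout.

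Footnote 3 points to the low end: "Window for all visits is during treatment is ± 2 days". Under three-monthly dosing, an injection given at a visit kept in window is also inside ±7 days.

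**4. Visits lost**

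Two-monthly visits over 12 months make 6 per man. For k = 3 the most that could be lost is 0.89 × 6 = 5.3, 1.76 × 6 = 10.6 or 4.28 × 6 = 25.7 visits per arm. Men who would have progressed in observation would lose fewer.

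**5. The 24-month proportion**

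Suppose m of 30 controls are dropped and the rest show proportion p. Restoring them moves the estimate by between −m·p/30 and +m·(1 − p)/30. The extremes need all m men to share one outcome.

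| m | p = 0.5 | p = 0.2 or 0.8 (largest) |
|---|---|---|
| 1 | ±1.7 points | 2.7 points |
| 2 | ±3.3 points | 5.3 points |
| 4 | ±6.7 points | 10.7 points |

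For scale, the 95% half-width at n = 30 is 1.96 × √(p(1 − p)/30): 17.9 points at p = 0.5 and 14.3 at p = 0.2 or 0.8.

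**The case against.** **The specific rule may simply govern.** It appears identically in three places, and the Amendment 6 log shows that the window was tightened deliberately. Read this way, the contradiction goes. The one-sidedness does not: it becomes settled policy.

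**Many late injections may fall under the existing exception.** A man injected late who carries on is arguably continuing hormonal therapy outside the protocol, and 7.5 would remove him anyway. This stands in part. The rules clearly part only for a man who misses the window and stops LHRHa.

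**Removal need not end all data collection.** Section 3.1 also takes progressors off study, yet 7.5 and 7.6 still seek their questionnaires. This stands for QOL. It offers nothing equivalent for PSA and testosterone.

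**No bias is shown.** Earlier censoring distorts a Kaplan-Meier or log-rank comparison only if it is informative. The documents give no reason to think that a missed window predicts progression. This stands; unequal follow-up by itself mainly costs precision.

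**Stronger readings to resist.** A reader might infer that the superiority test is compromised, because its control arm is the one exposed. That test is on FACT-P, and 7.5.6 seeks the Month-12 score from everyone who stops early. A reader might also infer that time to testosterone recovery is distorted between the superiority arms, but it is not compared between them.

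**Conclusion.** The point holds as a minor one. Whichever rule is intended, following the removal rule can shorten PSA and testosterone follow-up under LHRHa alone and never under ARN-509 alone. Other causes of lost follow-up, such as withdrawal or non-protocol therapy, can occur in any arm. In the combination versus LHRHa comparison both arms are exposed.

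Three exploratory secondary endpoints are affected, in an unknown direction and by an unknown amount. The figure of 0.9 to 4.3 removals rests on an assumed 1% to 5% miss rate and three later injections, and is not a bound. Even four dropped controls with the same outcome would move the 24-month proportion by less than its own 95% half-width. For the primary endpoint, the fall to 76.3% power needs four removals and complete loss of their Month-12 scores, which runs against 7.5.6. The documents do not support a claim of biased results or of material harm to the primary test.

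**What to change.** - **Protocol 7.5.2, footnote 5 and SAP 2.2.2.** Replace study removal with: *will discontinue protocol therapy, enter the Off-therapy Observation Period, and remain in follow-up*. PSA and testosterone then follow the two-monthly schedule. State that any outstanding Month-3 or Month-12 FACT-P is still collected at its calendar time from Day 1; the off-therapy schedule (7.2) has FACT-P only at Month 24 and at progression, so this must be written in.
- **Men who stay on or restart hormones.** Say that they are handled under the existing non-protocol-therapy rule. The change will not recover follow-up for them.
- **SAP 5.3.1.2.** State that a missed window alone is not a withdrawal, so men followed to 24 months stay in the denominator.
- **Reporting.** Give the number of missed windows by arm.

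The cost is a wording change and a few extra visits of a kind already scheduled. The protocol's Duration of Study entry says the last patient has already been consented, so the on-therapy wording may reach few men. The denominator rule and the by-arm count need only SAP text.

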7.5.3 ARN-509

Subjects randomized to either of the two ARN-509-containing arms will receive ARN-509 dosed orally on a daily basis with or without food. The starting dose of ARN-509 is 240 mg/day. With Amendment 7 (Version 8.0), subjects who are receiving the softgel capsules will switch to the tablet formulation. Ongoing subjects on a reduced dose of capsules should continue with that dose with lowest allowed dose being 120 mg (see Section 8). Dose delays and dose reductions will be permitted as per guidelines outlined in Section 9.2.

7.5.4 Concomitant Medications

Concomitant medications will be recorded at each monthly clinic visit. Subjects are recommended to take calcium 1000 mg/day and vitamin D (cholecalciferol) 800 IU/day in divided doses. Phosphodiesterase inhibitors such as sildenafil used to treat erectile dysfunction may be initiated or continued as per individual investigator discretion. Breast irradiation and/or tamoxifen to prevent and/or treat painful gynecomastia will also be permitted per individual investigator discretion. Subjects who require the initiation of bisphosphonate or other bone-targeted therapy (eg, those sustaining an osteoporotic fracture) while on study will be permitted to do so and remain on study, but subjects who have used a bone-modifying agent within 3 months prior to randomization will be excluded (see Section 4).

7.5.4.1 Prohibited Medications

No concomitant use of any anti-cancer therapy will be permitted. This will include surgery, radiation therapy, and other secondary hormonal therapies including first generation antiandrogens, 5-alpha reductase inhibitors (i.e. finasteride, dutasteride), megestrol acetate, immunotherapy, chemotherapy, or other investigational agents while on study [see Appendix 5 for list of prohibited treatments while on study]. Start of any of these therapies will result in discontinuation from the study, see Section 7.8. Nutritional supplements containing saw palmetto or pomegranate are also specifically prohibited.

7.5.4.2 ARN-509: Prohibited Medications:

As a class effect, androgen receptor antagonists have been associated with seizures due to an off-target mechanism of action (GABA_A inhibition). To date, no subjects receiving ARN-509 have experienced seizures, however, in preclinical experiments, at very high doses, dogs treated with ARN-509 had tremors and generalized seizures. Subjects will be closely monitored for seizures, but as a precautionary measure, the following drugs known to decrease the seizure threshold or cause seizure will be prohibited.

- Aminophylline, theophylline
- Atypical anti-psychotic drugs: clozapine, olanzapine, ziprasidone, bupropion
- Phenothiazine anti-psychotic drugs: chlorpromazine, mesoridazine, thioridazine
- Tricyclic and tetracyclic anti-depressants: amitriptyline, desipramine, doxipine, imipramine, maprotiline, mirtazapine (Remeron)
- Lithium
- Meperidine (Demerol) and pethidine

7.5.4.3 ARN-509: Restricted Medications:

If it is absolutely necessary for the well-being of the subject and alternative therapies are not available, these drugs should be used with caution and after discussion with [name] and the Sponsor's Medical Monitor. The list of medications that are prohibited or restricted while taking ARN-509, is provided in Appendix 5.

7.5.5 Safety Assessment

Subjects will be assessed for adverse events at each monthly clinic visit during the On-therapy Period. Adverse event collection starts with the signing of the ICF (see Section 7.1). Adverse events will be graded according to the National Cancer Institute (NCI)-Common Terminology Criteria for Adverse Events (CTCAE) Version 4.03 (available at <http://ctep.cancer.gov>). See Section 12.1.4 for attribution of adverse events. Dose modifications (interruptions, reductions or both) for ARN-509, will be allowed as per guidelines outlined in Section 9.2.

7.5.6 QOL

The FACT-P, EORTC QLQ-C30/QLQ-PR25, and SHIM questionnaires will be completed at the end of Month 3 and Month 12 or at the time of PSA or radiographic progression (if occurs before Month 12, every effort will be made to obtain the 12-month questionnaires for those who discontinue before 12 months).

